Combined peripheral (BreESTim) and central electrical stimulation (tDCS) for neuropathic pain management

NCT03302793

Version Date: 03/07/2016

University of Texas – Houston Medical School Protocol (CPHS HSC-MS-xxxx)

1. Protocol Title:

Combined peripheral (BreESTim) and central electrical stimulation (tDCS) for neuropathic pain management

2. Background:

Neuropathic pain is a chronic condition caused by a primary lesion or dysfunction of the nervous system. It is characterized by spontaneous, ongoing pain, described as burning, shooting, prickling or electrical, and/or pain in response to innocuous stimuli (allodynia) and exaggerated pain in response to noxious stimuli (hyperalgesia)(Bennett 2010). Neuropathic pain has increasingly been recognized as an important contributor to suffering, poor rehabilitation outcomes and reduced quality of life of the persons with SCI. Currently, there is no effective pharmacological treatment. Surprisingly, only 7% of responders reported pharmacological treatment is effective for neuropathic pain following SCI in a postal survey (Finnerup et al. 2001a). On the other hand, pharmacological interventions are often associated with side effects, such as addiction, withdrawal, and constipation, and sedation which may affect participation in rehabilitation and/or life activities, etc. Mechanisms of neuropathic pain are not well understood. Pain is multi-dimensional, including sensational and affective (i.e., unpleasantness) components. These components are processed in parallel, and inseparable to each other (Price 2000; Frot et al. 2008). For example, when superficial tactile stimulation is applied to the hand area where acupuncture points are located, activation is seen only in somatosensory cortices. However, when the acupuncture points are stimulated, and pain is experienced by the subjects, activation of additional cortical areas, such as anterior cingulate cortex (ACC) and insula, is observed(Hui et al. 2000). **Therefore, it is important that sensational and affective components of neuropathic pain could theoretically be modulated separately for therapeutic purposes.**

Among various neurostimulation techniques (Kotze and Simpson 2008), including transcutaneous electrical nerve stimulation (TENS) (Norrbink Budh and Lundeberg 2004), electroacupuncture (Ulett et al. 1998), spinal cord stimulation (Finnerup et al. 2001b), deep brain stimulation (Murphy and Reid 2001), transcranial direct current stimulation (tDCS) (Fregni et al. 2006; Boggio et al. 2008; Boggio et al. 2009) has emerged as a promising non-invasive brain stimulation technique for pain management. tDCS uses a small weak current applied through two oppositely charge electrodes on the scalp to induce neuroplastic changes that can alter pain perception in patients with chronic pain patients, such as SCI patients. Both electrodes are connected to a battery-powered device that induces a constant electrical current (usually, at 2mA) for approximately 15 to 20 minutes (Moreno-Duarte et al. 2014). The analgesic effect of tDCS depends on electrode placement, however. In a recent study(Boggio et al. 2008), **anodal tDCS targeting primary motor cortex (M1) increases pain as well as sensory perception thresholds.** while anodal tDCS of dorsal lateral prefrontal cortex (DLPFC) only increases pain threshold, without altering sensation thresholds. Anodal tDCS targeting M1 is believed to specifically modulate excitability of cortico-thalamic pathways, thus altering the sensational component of pain, while DLPFC stimulation arguably

operates at medial pain pathways through cortical-striatal-thalamic-cortical loop, as such attenuating the affective component of the pain (Plow et al. 2012). In a recent review in 2014 (Moreno-Duarte et al. 2014), there are eight clinical trials using various neurostimulation techniques for chronic pain management in SCI in the last 15 years. Among these studies, there were 3 tDCS, two TES (transcranial electrical stimulation), 2 rTMS (repetitive transcranial magnetic stimulation) and 1 TENS. Overall, the effect was heterogeneous. However, SCI patients were “responsive” to tDCS. Furthermore, the effect was better and longer-lasting when tDCS was combined with visual illusion in two studies (Soler et al. 2010; Kumru et al. 2013).

In summary, anodal tDCS targeting M1 will be selected since this approach influences sensational components of pain perception. BreESTim is shown to modulate the affective component of pain perception. Therefore, we expect that that combined BreESTim and tDCS treatment has addictive analgesic effects as compared to BreESTim or tDCS alone. We will test this treatment in healthy subjects and for neuropathic pain management in common patient populations, such as brain injury (BI), spinal cord injury (SCI), and amputation.

4. Description of Study:

This study has 4 experiments. The main idea is to test the effectiveness of the new intervention for neuropathic pain management for healthy subjects and one patient population (SCI, BI, or amputation) in each experiment. We request to recruit 20 subjects (5 subjects each group for healthy, SCI, BI and amputation). Overall, We plan to adopt recently published BreESTim (Li et al. 2013) and tDCS(Boggio et al. 2008) research protocols in this experiment. Briefly, this will be a single-center, randomized, cross-over trial to determine whether there is additive analgesic effect of a single session of combined and BreESTim and tDCS stimulation in healthy, and other patient subjects.

[figure not shown]
Subject recruitment

A total of 20 patients is planned to be enrolled as a pilot study for the following patient populations: healthy, BI, SCI and amputation. The estimated number of total patients will be calculated based on our pilot study with 5 subjects for each group. Patient subjects will be screened at the outpatient clinic of TIRR Memorial Hermann Hospital. Subjects will be recruited and enrolled in the project if they meet the inclusion and exclusion criteria (see subject population).

The interventions/Experimental procedures

The experiment consists of 3 sessions, including 1) BreESTim + Sham tDCS (i.e., BreESTim only), 2) BreESTim +active tDCS, and 3) tDCS only. Three sessions will be conducted on three different days with an interval of at least 24 hours. In each session, a conditioning tDCS (active or sham) will be performed first, then followed by BreESTim.

Anodal tDCS targeting M1 (Boggio et al. 2008) will be used. During each session, subjects will receive either active or sham stimulation to M1. A pair of surface sponge electrodes (35cm^2) will be soaked in saline and applied to the scalp. The anode electrode will be placed over C3 according to the 10-20 system for EEG electrode placement. The reference cathode electrode will be placed over the supraorbital area on the opposite side. For all active tDCS conditions, DC will be delivered by a specially developed, battery-driven, constant current stimulator

(Soterix Medical, NY) with a maximum output of 10mA. A constant current of 2 mA will be applied for 15 min (the effect is usually expected to last 1-2 hours after tDCS) (Boggio et al. 2008). After the 15-min tDCS (active or sham), BreESTim will follow immediately.

Figure 1 The experimental setup with BreESTim

The same BreESTim protocol (Li et al. 2013) will be used. Briefly, subjects will wear

facemask that will be connected to a Pneumotach system to record breathing signals. Surface electrodes will be trimmed to be applied to acupuncture points (Neiguan and Weiguan) (see Figure for experimental settings). In the BreESTim treatment, a single-pulse (0.1 ms square wave) electrical stimulation is delivered to

acupuncture points when subjects are taking a fast, strong, and deep inhalation, similar to a deep breath but faster and stronger. It is important to mention that subjects control the intensity of electrical stimulation, to increase the intensity as tolerated gradually. Subjects will be explicitly instructed that aversiveness of painful stimulation is part of treatment protocol. To standardize, the total number of electrical stimuli is 200. Sufficient rest time will be allowed during the treatment. The BreESTim treatment takes about 30 minutes.

The above intervention will be applied to the following subject populations:

Experiment 1: the effect of combined BreESTim and tDCS treatment in healthy subjects

Experiment 2: the effect of combined BreESTim and tDCS treatment on neuropathic phantom pain in amputation subjects

Experiment 3: the effect of combined BreESTim and tDCS treatment on neuropathic pain in SCI subjects

Experiment 4: the effect of combined BreESTim and tDCS treatment on neuropathic pain in BI subjects

Specimens:

No specimens will be collected

5. Subject Population

In experiments 1-4, **5** subjects for each population (healthy, SCI, BI, and amputation) will be recruited and tested. An estimated number of patients will be obtained after the pilot study.

In experiment 1, healthy subjects will be recruited from residents, staff, therapists at TIRR Memorial Hermann in response to the flyer. The following inclusion/exclusion criteria will be followed (1) age between 18 and 60 years, (2) no clinically significant or unstable medical, neuropsychiatric, or chronic pain disorder, (3) no history of substance abuse or dependence, (4) no use of central nervous system-effective medication, (5) no history of brain surgery, tumor, pacemaker, or intracranial metal implantation or atrial fibrillation.

Patient subjects will be recruited from the TIRR outpatient clinic for experiments 2-4 for a total of 15 subjects.

Inclusion criteria: A patient who 1) has neuropathic pain after traumatic spinal cord injury or amputation or brain injury; 2) has chronic pain, >3 months; 3) is between 18 to 75 years of age; 4) is stable on oral pain medications at least two weeks. Patients are allowed to continue their pain medications, i.e., no change in pain medications.

Exclusion criteria: Patients will be excluded if they 1) are currently adjusting oral pain medications for their neuropathic pain; 2) have pain, but not neuropathic, e.g., from inflammation at the incision wound of the residual limb

or neuroma; 3) have a pacemaker in order to avoid possible side effects of electrical stimulation; 4) have amputation in their arm(s); 5) have SCI involving impairment of arms; 6) are not able to follow commands, or to give consent; 7) have asthma or other pulmonary disease; 8) are not medically stable; 9) have preexisting psychiatric disorders; 10) alcohol or drug abuse.

6. Data Analysis

Pre-intervention and post-intervention measurements include electrical sensation and pain thresholds and warm sensation and heat pain thresholds as used in our recent study (Li et al. 2013). In addition, visual analogue scores (VAS), modified visual analogue scores (mVAS) will be recorded in patient subjects. These measurements will be taken pre- and post-intervention for both sessions. VAS has been extensively used and validated (McCarthy et al. 2005). mVAS further quantifies the effect of pain reduction by measuring duration and amount of change in VAS, i.e., how much pain was reduced and how long it lasted (reduction × hours). It is necessary to note that pain rating is very subjective. This cross-over design uses subjects as their own control.

Heart rate variability as objective outcome measurements

We have been searching for non-invasive objective pain outcome assessment. Heart rate variability has recently recognized a physiological marker for pain assessment (Cowen et al. 2015), see also Appelhans & Leucken 2008 (both articles are uploaded to the iRIS).

We propose to add 5 minutes of Heart Rate recordings before and after the interventions. Experimental procedures and data analysis will be adopted from the above articles.

Two-way repeated measures ANOVA with factors INTERVENTIONS (3 levels, BreESTim only, tDCS only and tDCS+BreESTim) and TIME (pre- and post-intervention) will be used determined statistical significance for each threshold (electrical sensation and pain thresholds, and thermal sensation and pain threshold, mVAS). It is expected that BreESTim + tDCS will have better analgesic effect than BreESTim or tDCS alone.

7. Potential Risks/Discomforts:

The risks associated with this study are minimal. Electrical stimulation has been used extensively in clinical settings. Patients may feel uncomfortable, or even painful during electrical stimulation. The patients will be specifically instructed that they are encouraged to increase the intensity of electrical stimulation to the level they may feel uncomfortable, but they need to be able to tolerate at that level if given repetitively. They are also explicitly instructed to decrease the intensity of electrical stimulation if they cannot tolerate it. Surface electrodes can cause skin irritation from the tape adhesive or the electrode paste. Breathing through a face mask may be make patients feel uncomfortable. All tested subjects in the previous studies (approximately 70 subjects, including patients) tolerated the mask well.

All the tDCS safety papers ([poreisz 2007](#)-

<http://www.ncbi.nlm.nih.gov/pubmed/17452283>, [kessler 2011](#)-

<http://www.ncbi.nlm.nih.gov/pubmed/22037128> , [nitsche 2003](#)-

<http://www.ncbi.nlm.nih.gov/pubmed/14580622>) point to adverse effects as

itching/tingling. Over 600 studies have published using tDCS and Soterix units operate within the established current intensities/durations (0-2 mA, 10-40 min).

8. Benefits:

There are several potential benefits in this study: 1) direct benefit to subjects as their neuropathic pain may be relieved by the intervention; 2) benefit to the class of subjects: other patients in the same patient population may be benefit if the intervention is applied to them; 3) adding to the knowledge base: the findings will be definitely added to the knowledge base. Specifically, the study will provide evidence of an alternative and innovative intervention for neuropathic pain management.

9. Risk-benefit Ratio:

In view of the minimal risk, benefits and the knowledge to be gained far outweigh the risks.

10. Consent Procedures:

Informed consent will be obtained from the subject at the Motor Recovery Laboratory (B-107) at TIRR Memorial Hermann. After a subject is identified and interested in participating, informed, written consent will be obtained by the study coordinator.

11. Confidentiality Procedures:

In order to minimize risk to confidentiality, all data will be de-identified, coded with a study specific identification number, maintained on a password-protected server, and/or kept in a locked office. No findings will be released without written authorization by the subject.

12. Costs:

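### The order of the three sessions has no stated method of generation or balance, and the analysis has no session term, so with five subjects per experiment a change in response over sessions can bias the comparison of interventions

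*Combined protocol and SAP*

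**What the plan says.** Section 4 (Description of Study) calls the trial randomized and cross-over, and that is all the supplied text says about order: "this will be a single-center, randomized, cross-over trial to determine whether there is additive analgesic effect of a single session". No sequences, blocking or balance are given.

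The size is fixed in the same section, "We request to recruit 20 subjects (5 subjects each group for healthy, SCI, BI and amputation", and Section 5 (Subject Population) repeats it for the patients: "Patient subjects will be recruited from the TIRR outpatient clinic for experiments 2-4 for a total of 15 subjects".

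Under the interventions heading of Section 4, "The experiment consists of 3 sessions, including 1) BreESTim + Sham tDCS", followed by the combination and tDCS only. On spacing: "Three sessions will be conducted on three different days with an interval of at least 24 hours". In the BreESTim procedure, "subjects control the intensity of electrical stimulation, to increase the intensity as tolerated gradually".

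Section 6 (Data Analysis) relies on within-subject comparison: "This cross-over design uses subjects as their own control". The planned test is a two-way repeated measures ANOVA with factors INTERVENTIONS (three levels) and TIME (pre, post), applied to the sensation and pain thresholds and to mVAS. It has no factor for session number or sequence.

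**The concern.** Using subjects as their own controls removes differences between people. It does not remove differences between a person's first, second and third session. Those are dealt with either by spreading the interventions evenly over the sessions or by putting session in the model, and the supplied text states neither.

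A change in response over sessions is plausible from the protocol's own procedures. Subjects raise a painful stimulus themselves, so what they tolerate, and hence the stimulation they receive, may differ at a later visit. Sessions may be only a day apart.

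Each population is its own experiment of five, so an uneven set of orders does not average out at the level where the comparison is made. Section 4 also says the pilot will be used to calculate the eventual number of patients, so a distorted estimate would carry into the next study.

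**Working it through.** **Inputs from the protocol.** Five subjects in each of four experiments: 4 × 5 = 20 in total and 3 × 5 = 15 patients, which matches the stated figures. Three sessions give 3! = 6 possible orders. No power, SD or alpha is stated, so there is no further figure to reproduce.

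**Assumptions.** (a) Each subject's order is drawn independently, with all six equally likely. (b) The response (post minus pre) drifts linearly by *b* within-subject SD per session, with *b* from 0 to 1.5. (c) The test is at 5%. The documents give none of these.

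**1. How uneven would the orders be?** All 6^5 = 7,776 allocations were enumerated.

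- The combination is first for at least 3 of 5, or last for at least 3 of 5: 2 × P(Bin(5, 1/3) ≥ 3) = 2 × (40 + 10 + 1)/243 = 102/243 = 42.0%. At least 4 of 5: 2 × 11/243 = 9.1%.
- Position gap between the combination and BreESTim only, per subject: ±1 (four orders) or ±2 (two orders). Its variance is (4 × 1 + 2 × 4)/6 = 2. The mean over five subjects has SD √(2/5) = 0.63 sessions and mean absolute value 0.508.
- That mean gap is at least 0.6 sessions in 3,396/7,776 = 43.7%, and at least one full session in 1,236/7,776 = 15.9%.
- Every intervention falls in every position once or twice, the most even result possible with five, in 900/7,776 = 11.6%.

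**2. Which session changes matter?** With two levels of TIME, the INTERVENTIONS × TIME test is a test on post minus pre. If session *s* adds the same amount to both, (post + shift) − (pre + shift) = post − pre, and the shift cancels. It does not cancel in the INTERVENTIONS main effect. A drift in the response itself, including in mVAS (reduction × hours), does not cancel.

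**3. Size of the bias.** Mean absolute bias in a pairwise difference = *b* × 0.508.

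| *b* (SD per session) | Mean absolute bias (SD) | False positives, all draws | False positives, largest gap ≥ 1 session (37% of draws) |
|---|---|---|---|
| 0.5 | 0.25 | 5.1% | 7.8% |
| 1.0 | 0.51 | 5.4% | 12.3% |
| 1.5 | 0.76 | 5.8% | 15.1% |

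The false-positive rates come from 100,000 simulated experiments per value of *b*, with no treatment effect and no session term.

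**4. Five of the six orders, once each.** Over all six orders each intervention's positions sum to 2 × (1 + 2 + 3) = 12. Leaving out one order makes the mean gap between two interventions (difference of their positions in the omitted order)/5, which is ±0.2 or ±0.4. The mean square is 2/25 = 0.08, so the RMS is 0.28. Against 0.40 for independent draws, 0.08/0.40 = 0.20, or 80% less bias variance.

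**5. Balance over the patients.** Write C for combined, B for BreESTim only and T for tDCS only. Three full sets of six orders put each intervention in each position 3 × 2 = 6 times. CBT, BTC and TCB form a Latin square, so omitting them removes each intervention from each position once: 6 − 1 = 5.

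**6. Why a session term is also needed.** With five distinct orders and no session term, the trend stays in the error: the false-positive rate falls to 3.0% at *b* = 0.5 and 0.7% at *b* = 1. With session as a three-level factor, simulation returns about 5% at every *b* tried. Error degrees of freedom go from 15 − 1 − 4 − 2 = 8 to 8 − 2 = 6.

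**The case against.** The strongest objection is that independent draws are assumed, not documented. Section 4 describes the design in brief and adopts published procedures that were not available here. A figure next to the design paragraph and a stretch of background text were also missing. A reader might infer that the orders are known to be unbalanced. The documents do not support that; the supportable statement is that the supplied text does not specify how order is set.

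A reader might also infer that any trend over sessions enters the comparison. It does not: a shift common to pre and post, such as growing used to the threshold tests, cancels in the interaction. Nor is there a general inflation of false positives, since averaged over all draws the rate is 5.1% to 5.8%.

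Nothing in the documents gives the size of a session effect, so the bias cannot be stated in VAS points, and plain VAS is not among the outcomes listed for the ANOVA. Counts that include the middle session would look worse (the combination in one same position for 4 or 5 subjects in 13.6% of draws), but a middle position gives no early or late shift.

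Finally, this is a pilot, which lowers the weight of any significance test. All of these limits stand. They narrow the point without removing it, because neither the stated design nor the stated analysis deals with a drift in response.

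**Conclusion.** The point holds as a gap in both design and analysis that should be closed before enrolment. If orders are drawn independently, an experiment of five will often have the combination placed unevenly: first, or last, in at least 3 of 5 subjects in 42% of experiments, and a full session or more from BreESTim only, on average, in 16%. If the response also drifts by 0.5 to 1.5 SD per session, the typical bias in a pairwise difference is 0.25 to 0.76 SD, and the planned model cannot detect or correct it.

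Both conditions are assumptions. With no drift in response the interaction is unbiased whatever the orders. If the sponsor already balances order, a sentence saying so settles the design half, and the missing session term remains.

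**What to change.** 1. In each experiment, assign five of the six orders once each, in random sequence, from a prepared list kept concealed until the subject is enrolled. Across the three patient experiments omit CBT, BTC and TCB in turn, so that each intervention occurs five times in each position over the 15 patients. For the healthy experiment any one order may be left out. State this in Section 4.
2. In Section 6, add session number (1, 2, 3) as a factor in the analysis of each outcome.

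The list caps the pairwise position gap at 0.4 sessions. The session term removes the remaining trend and keeps the test near its nominal level.

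**Cost:** a list of 20 orders and two error degrees of freedom per experiment (8 to 6), with no added subjects, visits or procedures. The last subject's order in an experiment is partly predictable to someone who knows the earlier ones; this matters little because every subject receives all three interventions. The change does not by itself remove carry-over from one session to the next.

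### The stated aim of an additive effect cannot be estimated from three sessions; the design can show only whether the combination beats each single treatment, and the planned ANOVA does not by itself test that

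*Combined protocol and SAP*

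**What the plan says.** Section 4 gives the purpose of this randomized crossover study: "to determine whether there is additive analgesic effect of a single session of combined and BreESTim and tDCS stimulation". The sessions are listed as "1) BreESTim + Sham tDCS (i.e., BreESTim only), 2) BreESTim +active tDCS, and 3) tDCS only". Sham is described for tDCS ("During each session, subjects will receive either active or sham stimulation to M1"). No sham is described for BreESTim, which delivers 200 stimuli over about 30 minutes and is introduced to subjects this way: "Subjects will be explicitly instructed that aversiveness of painful stimulation is part of treatment protocol".

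Section 4 also says: "In each session, a conditioning tDCS (active or sham) will be performed first, then followed by BreESTim". That does not fit a session called tDCS only.

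Section 6 plans a two-way repeated measures ANOVA with "factors INTERVENTIONS (3 levels, BreESTim only, tDCS only and tDCS+BreESTim) and TIME (pre- and post-intervention"). It names no contrasts between sessions. The anticipated result is: "It is expected that BreESTim + tDCS will have better analgesic effect than BreESTim or tDCS alone". The summary paragraph just before section 4 says much the same, expecting an additive effect (printed as *addictive*) relative to either treatment by itself.

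**The concern.** Additivity of two treatments is a statement about four conditions: both, each one alone, and neither. The trial runs three of them. If the aim is carried into the report as worded, a favourable result would be described as an additive effect that these data cannot establish.

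There is a second gap. The claim the design can support, that the combination is better than each component, needs two specific comparisons. Section 6 offers an overall three-level test in their place.

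The two comparisons also differ in kind. The combination and the BreESTim session both contain BreESTim and differ in active versus sham tDCS. The combination and the tDCS-only session differ by an entire painful procedure with no sham counterpart, so a gain there may include expectation and attention effects.

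**Working it through.** The documents state no figure on this point, so the check is one of estimability.

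**Inputs.** The session list in section 4 and the three ANOVA levels in section 6. The tDCS-only session is taken to contain no BreESTim.

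**Notation.** For the mean pre-to-post change, larger meaning more analgesia, let m be the change with neither treatment active (placebo response, repeat testing), a the tDCS effect, b the BreESTim effect, and ab the departure from additivity.

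- BreESTim + sham tDCS: B = m + b
- tDCS only: T = m + a
- Combination: C = m + a + b + ab

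**Step 1: what can be estimated.** The three rows have rank 3 for four parameters.

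- C − B = a + ab: estimable, and m cancels
- C − T = b + ab: estimable, and m cancels if it is common to the sessions
- C − B − T = ab − m: equals ab only if m = 0
- a, b and ab separately: not estimable

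Illustration with assumed changes B = 3, T = 3, C = 5. Then ab = C − B − T + m = −1 + m.

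| Assumed m | a | b | ab | Reading |
|---|---|---|---|---|
| 0 | 3 | 3 | −1 | sub-additive |
| 1 | 2 | 2 | 0 | additive |
| 2 | 1 | 1 | +1 | super-additive |

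The same session means support all three readings, and more subjects would not change that. A both-sham session (row = m) would raise the rank to 4 and make ab = C − B − T + N estimable, where N is that session's mean change.

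**Step 2: what the ANOVA tests.** The INTERVENTIONS main effect averages over pre and post, and the TIME main effect averages over sessions. Only the interaction compares changes, and its null hypothesis is B = T = C. Take assumed changes B = 3, T = 1, C = 2. The mean is 2, and the sum of squared deviations is 1 + 1 + 0 = 2. The B-versus-T difference alone gives (3 − 1)²/2 = 2, which is all of it. Yet C − B = −1 and C − T = +1, so the combination does worse than BreESTim. A significant interaction is therefore compatible with no advantage of the combination over one of its components.

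**Step 3: the conflicting session text.** If BreESTim follows tDCS in every session, the third session becomes m + a + b + ab, identical to the combination. The rank falls to 2 and only C − B is informative.

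**Step 4: would a fourth session help at this size?** Assume independent session changes with a common SD and a two-sided 5% t test. The contrast SD is then 2 SD for ab and √2 SD for a pairwise contrast. For a true value of 1 SD:

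| n | Power, ab with four sessions | Power, one pairwise contrast |
|---|---|---|
| 5 (one population) | 14% | 23% |
| 20 (all pooled) | 57% | 85% |

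For 0.5 SD, power for ab is 7% and 19%; for a pairwise contrast it is about 10% (0.095) and 32%. The SD ratios are assumptions, since the documents give no SD or effect size, and section 6 does not say that the populations would be pooled.

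**The case against.** The strongest reply is that the authors use the word loosely. The summary before section 4 and the expectation in section 6 both explain it as better than either treatment alone, and three sessions can address that. This stands. A reader might infer that the trial cannot answer its question at all; the documents do not support that. It also means that rewording, and not an added session, is the proportionate remedy.

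A reader might also infer that the missing session biases the planned results by some number of pain-scale points. It does not. The contrast C − B − T appears nowhere in the plan, and a non-specific change common to the sessions cancels in the pairwise comparisons.

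Nor do the documents require that the combination versus BreESTim + sham tDCS be the sole primary contrast. That is a preference, since it tests only what tDCS adds. The available text does not describe the sham tDCS procedure or mention blinding, so that comparison should not be oversold either.

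On subjectivity, section 6 makes its remark about pain ratings, and it also plans thresholds and heart rate variability, the latter offered as objective. The expectation concern applies most directly to the ratings.

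Finally, the design figure and part of the text before section 4 could not be seen, so no sham BreESTim *described* is not proof that none exists. The session list and ANOVA levels are nonetheless explicit. The pilot purpose does not remove the point, because the later sample size is to be calculated from this pilot and needs a defined comparison.

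**Conclusion.** The point holds as a mismatch between the stated aim, the design and the analysis. Additivity is not estimable: rank 3 for four parameters, with ab and m confounded. Superiority of the combination to each component is estimable, but the three-level interaction is not a test of it. No numerical bias in the planned comparisons is claimed; the size of the problem is that one stated conclusion is unavailable and the other lacks its test.

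This rests on the third session containing no BreESTim, on analysis of pre-to-post change, and on there being no further session in the unseen figure. It should be corrected before results are reported or used for sample size planning.

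**What to change.** 1. In section 4, and in the summary sentence printed as *addictive*, replace the additive wording with: *greater analgesic effect than BreESTim alone and than tDCS alone*. Make no claim of additivity or synergy.
2. In section 6, state that this conclusion requires both pre-to-post change contrasts to favour the combination: combined minus BreESTim + sham tDCS, and combined minus tDCS only. Test each at the full two-sided level; because both must succeed, this conclusion needs no adjustment for having two contrasts. Alternatively, for the pilot, report each with its confidence interval.
3. Label combined versus tDCS only as a comparison without a sham BreESTim, whose gain may include expectation and attention effects.
4. Reconcile the statement that BreESTim follows tDCS in each session with the tDCS-only session.

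The cost is a narrower claim, the rewording of two sentences, a short addition to section 6 and a clarification of the session description. No extra session or subjects are needed.
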